### 3.3 The Clinical Appointment

Patients will be asked to attend a clinical appointment at Chelsea and Westminster Hospital, which will last approximately one hour and 45 minutes. At the clinical appointment a number tests will be performed. These are summarised in the table below.

Clinical Parameter	Process	Time taken to complete (minutes)	Core or specific
Collection of patient demographics	Analysis of patient notes and history taking	5	Core and specific
Structured neurological examination including blood pressure	Examination	10	Specific
Quantitative Sensory Testing (QST)	Psychophysical testing	30	Specific
CHANT : Clinical HIV-Associated Neuropathy Tool	History and examination	5	Core
QUESTOR body map	Body map representation of pain	2	Core
DN4-i : Doleur Neuropathique 4 Interview	Interview	3	Core
'CogState' cognitive function testing	Computer Based test	45	Specific
Peripheral Blood Sample	Blood Sample	5	Core

Table 2. Summary of tasks to be performed at clinical appointment

#### a) Gathering of patient information

Information will be collected from the patient interview, and from prior analysis of paper and electronic medical records. The following will be documented:

- Gender, age, ethnicity, sexual orientation
- Hand dominance
- Medical history including other potential causes for neuropathy and neurocognitive impairment
- Date of HIV diagnosis, complications, drug history including previous and current ART regimens
- Drug, smoking and alcohol history – both chronic and within the last 48 hours
- Educational level, occupation and socioeconomic status

- Results of clinical investigations previously performed:
  - Nerve conduction studies, QST and skin biopsy (where available)
  - Most recent CD4 count and viral load and CD4 nadir
  - LFTs/TFTs/B12/triglyceride levels/HepB/HepC/syphilis
  - CT/MRI/PET imaging of the brain (where available)

*b) Basic examination*

- Height
- Weight

*c) Structured Neurological Examination*

An upper and lower limb neurological examination will be performed to detect for clinical neuropathy. This will include an assessment of light touch and pinprick sensation, joint position and vibration sensation, deep tendon reflexes, muscle wasting and motor power, as described by the NeuPSIG guidelines [55].

A lying and standing blood pressure will be measured as an indicator of autonomic dysfunction. A lying non-invasive blood pressure will be recorded after lying for 5 minutes. The patient will be asked to stand and their blood pressure recorded at 1 and 3 minutes. A diagnosis of orthostatic hypotension will be made if there is a fall in systolic pressure of at least 20mm Hg or diastolic pressure of at least 10mm Hg [56]

*d) Case Definition: Diagnosis of HIV-SN*

All patients will be screened for HIV-SN based on the CHANT (Clinical HIV-associated Neuropathy Tool) screening tool [15]

This is a simple 4-item tool comprised of two subjective questions (self report of foot pain and of foot numbness), and two objective measures on clinical examination (loss of vibration sense and loss of ankle reflex). If the patient is positive for one symptom and one sign in a bilateral distribution they will be defined as having sensory neuropathy.

*e) Diagnosis of HIV-SN related neuropathic pain (HIV-SNP)*

Patients will be given a body map to illustrate any sites of pain, and the 7-item DN4-i (Douleur Neuropathique 4-interview) interview will be conducted to identify the probability of the patient having neuropathic pain. A score of  $\geq 3$  out of 7 from the patient reported outcome section of the DN4-i will be used as a positive diagnosis of neuropathic pain [57] as this cut-off has been shown to have sensitivity of above 80% in neuropathic pain conditions[58].

Patients will also be asked to indicate the areas that they experience pain. Symptoms must also be in a neuroanatomically plausible distribution, which could be attributable to HIV-SN; for example in a distal, symmetrical distribution. A QUESTOR legend for body areas will be used for this. Both a score of  $\geq 3$  on DN4-i and a plausible anatomical distribution will be required for definition of HIV-SNP.

*f) Neurocognitive Assessment*

- Although full neuropsychological testing is the gold standard for the diagnosis of HAND [60], it is very time consuming and requires specialist delivery which is not universally available. It is also used for the diagnosis of HAND rather than the measurement of it,

and such quantification of the disorder is important for this study, and for longitudinal follow up of patients. One computerised battery of tests (CogState) has been studied in HAND and has been shown to have a positive predictive value of 81%[61]. It also appears to be sensitive enough to monitor changes in ARV therapy and mirrors structural changes identified on MRS[62]. It includes eight tasks conducted with a computer screen and keyboard. There is a 15 minute 'training session' and the test takes approximately 20 minutes. It assesses eight attention, memory and executive function domains (**specific phenotyping**).

- A baseline level of intelligence quotient, such as the National Reading Test has not been included as it is not a longitudinal study and would not accurately assess IQ in such a multicultural population where English is frequently not the first language.
- A subjective measure of cognitive function will also be performed using the Everyday Memory Questionnaire (EMQ). This provides a patient reported measure of memory and attention to compare with the objective computerised measure.

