#### *g) Quantitative Sensory Testing (specific phenotyping)*

Quantitative Sensory Testing (QST) will be conducted the German Research Network on Neuropathic Pain QST protocol [10]. This is a battery of somatosensory testing which uses mechanical, cold, warm and pinprick stimuli in 13 domains; detection thresholds (cold detection threshold (CDT), warm detection threshold (WDT), paradoxical heat sensation (PHS), thermal sensory lime (TSL), mechanical detection threshold (MDT) and vibration detection threshold (VDT)), pain thresholds (cold pain threshold (CPT), heat pain threshold (HPT), mechanical pain threshold (MPT) and pressure pain threshold (PPT)), and stimulus-response functions (mechanical pain sensitivity (MPS), wind-up ration (WUR) and dynamic mechanical allodynia (DMA)).

Full QST testing has been performed on patients with HIV-SN in a previous study [14]. This study showed that although 86% of HIV-SN patients showed a loss of function in at least one modality, no single sensory parameter was had a useful diagnostic utility. This study showed that there were no significant differences in CPT, DMA, MPT and MPS between those with HIV-SN and healthy controls, and between those who reported pain and those that did not. Other studies have however, highlighted MPT and MPS as useful parameters [49] in HIV-SN. Therefore, in this study, the full DFNS QST protocol will be performed. The testing will be performed at the site of maximum pain or, in those with no pain, on the dorsum of their right foot, in the S1 dermatome.

QST results have been shown to differ in populations with cognitive impairment, such as Alzheimer's disease [63], but have not been assessed in comparison to mild cognitive impairment in HIV. It has however, been shown that there is good test-retest correlation when conducting QST in mild to moderate Alzheimer's, indicating that despite the requirement for short term memory and other executive functions, QST can still be performed in a reliable manner [63].

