### **3.4 Study Outcome Measures**

The aim of the HIV-POGO study is to phenotype a cohort of HIV positive patients with and without HIV-SN and to identify factors associated with neuropathy and, in patients with neuropathy, factors associated with neuropathic pain. It is anticipated that genetic analysis will show differences between the phenotyped groups. We also aim to elucidate any neurocognitive impairment in the cohort and to examine whether there is any correlation with the HIV-SN phenotype or with how pain is reported.

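### Foot pain can qualify a patient for HIV-SN, so the painful v painless contrast within HIV-SN is biased downward for numbness and anything tied to it

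*Combined protocol and SAP*

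**What the plan says.** Section 3.3 d) uses the four-item CHANT tool. The symptoms are "self report of foot pain and of foot numbness". The signs are "two objective measures on clinical examination (loss of vibration sense and loss of ankle reflex". One of each is enough: "If the patient is positive for one symptom and one sign in a bilateral distribution they will be defined as having sensory neuropathy".

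Section 3.4 sets the aim of finding "factors associated with neuropathy and, in patients with neuropathy, factors associated with neuropathic pain".

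Section 3.3 e) defines painful neuropathy (HIV-SNP) separately, by a DN4-i score of at least 3 together with location: "a plausible anatomical distribution will be required for definition of HIV-SNP". The CHANT foot-pain item is not itself the pain outcome.

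Sensory function is measured in detail (section 3.3 g): "Therefore, in this study, the full DFNS QST protocol will be performed".

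Section 7.2 covers genetic analysis only. It gives no plan for the painful v painless contrast, no alternative case definition, and no mention of how the entry rule bears on that contrast.

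**The concern.** The study wants to separate what drives neuropathy from what drives pain, but one of the two symptoms that admit a patient to the neuropathy group is pain. Looking for pain factors inside that group conditions on having pain or numbness. Even if the two are unrelated in the population, they become inversely related among those selected.

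A factor that only increases numbness is then pushed towards appearing protective against pain. A factor that only increases pain raises the chance of being called HIV-SN, so it is pushed towards appearing to be a neuropathy factor. Both errors fall on the distinction that section 3.4 sets out to make. Analysing pain only within neuropathy is no safeguard, because that restriction is what produces the first error.

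**Working it through.** The documents give no sample size, power or effect size for painful v painless, so there is no stated figure to reproduce.

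**Inputs from the documents.** Entry rule (3.3 d): (foot pain or numbness) and (vibration loss or ankle-reflex loss), bilateral. Pain outcome (3.3 e): HIV-SNP. Cohort (3.1): 200. HIV-SN prevalence (section 1): about 40%, range 20% to 57%. Share of HIV-SN with pain (section 1): 38% to 90%.

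**Assumed.** Among sign-positive patients, foot pain p = 50%, independent of numbness. Numbness is n0 without a factor and n1 with it, and the factor has no effect on pain. A fraction q of foot-pain patients meet HIV-SNP, regardless of numbness; patients without foot pain do not meet it. The documents give no value for p, n0, n1 or q.

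**1. What the rule forces.** HIV-SN without foot pain means numbness plus a sign, so numbness is 100% in that group whatever the truth. With foot pain, numbness can take any value. The sign-positive, pain-free, non-numb cell is empty.

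**2. Split by foot pain.** P(pain | HIV-SN) = p / [1 − (1 − p)(1 − n)].
- n0 = 40%: 0.5/0.7 = 0.714, odds 2.5.
- n1 = 60%: 0.5/0.8 = 0.625, odds 1.667.
- Odds ratio = 1.667/2.5 = 0.67, where the truth is 1.

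The odds ratio reduces to n0/n1 for any p: 45% to 55% gives 0.82, and 30% to 60% gives 0.50.

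**3. Split by HIV-SNP.** Replace the numerator by q·p.
- q = 80%: 0.4/0.7 = 0.571 (odds 1.333) and 0.4/0.8 = 0.500 (odds 1). Odds ratio 0.75.
- q = 60%: 0.3/0.7 = 0.429 (odds 0.75) and 0.3/0.8 = 0.375 (odds 0.60). Odds ratio 0.80.

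**4. Higher baseline numbness.** Raising numbness from 70% to 84% is the same odds ratio for numbness (2.25) as 40% to 60%. Foot pain: 0.70/0.84 = 0.83. HIV-SNP: 0.87 (q = 80%) or 0.89 (q = 60%).

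**5. False positives.** 200 × 40% = 80 HIV-SN cases, taken as 40 v 40. Two-sided two-proportion test at 5%, exact binomial enumeration, numbness 40% to 60%:
- Factor present v absent: 13% (foot pain), 11% (HIV-SNP, q = 80%), 8% (q = 60%).
- Painful v painless, factor carried by half of sign-positive patients: 16%, 11% and 9%.

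So roughly 8% to 16%. With numbness 70% to 84% the same calculation gives about 6% to 8%.

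**6. Leak into neuropathy v none.** A factor raises foot pain from 40% to 60%; numbness is 50% either way.
- Among sign-positive patients, P(HIV-SN) = 1 − 0.6 × 0.5 = 0.70 and 1 − 0.4 × 0.5 = 0.80. Odds ratio = 4/2.333 = 1.71.
- Whole cohort, if half have a sign: 0.35 and 0.40. Odds ratio = 0.667/0.538 = 1.24.

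**7. Measured sensory loss.** Simulation of 1.5 million subjects with a latent severity. Assumed: each sign 35% prevalent and correlated 0.7 with severity; sensory-loss score correlated 0.7; numbness 25% to 40%, correlated 0.3 to 0.7; foot pain 30% to 50%, correlated 0 to 0.6. Standardised difference in sensory loss, painful minus painless:
- Pain unrelated to severity: 0.00 if signs alone define neuropathy. Under the CHANT rule, −0.13 to −0.38 (foot pain) or −0.07 to −0.31 (HIV-SNP, q = 80% or 60%).
- Pain rising with severity (foot-pain split): +0.16 becomes +0.04 to −0.22; +0.33 becomes +0.21 to −0.05; +0.52 becomes +0.41 to +0.15.

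The shift was downward in all 36 scenarios.

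**The case against.** **The pain outcome is HIV-SNP, not the CHANT item.** Foot-pain patients scoring below 3 on DN4-i join the comparison group and need not be numb. It is therefore wrong to infer that the protocol's non-HIV-SNP group is 100% numb, or to take 0.67 as the size for the planned contrast. This stands: 0.75 to 0.80 is the better illustration. The documents also do not list the DN4-i items, so whether numbness itself raises the score, and what that does to the net bias, cannot be settled from them.

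**A built-in false inverse link between sensory loss and pain.** A reader might infer this, but it is too strong. The effect is certain only for self-reported numbness split by foot pain. For QST and signs it depends on their correlation with numbness. If pain truly rises with severity, the observed link may only be shrunk.

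**Larger false-positive rates.** The same calculation gives 27% at 100 v 100, but that would need all 200 participants to have HIV-SN, and the cohort must include patients without it. Section 3.1 does target patients with known neuropathy, so cases may exceed 80, but that figure should not be used.

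**Scope.** The only analysis specified is genetic replication for pain phenotypes, with no stated contrast within HIV-SN. That is fair, but section 3.4 sets that contrast as an aim. The leak into neuropathy v none is limited by the sign requirement and by the exclusion in section 4.3 of patients scoring 4 or more for pain of other origin. Neither removes it.

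**Conclusion.** The concern holds. Following sections 3.3 d) and 3.4 as written biases the within-HIV-SN pain contrast downward for numbness and for factors or measures tied to it, and lets pain-only factors leak into neuropathy v none. Nothing in section 7.2 corrects either.

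The mechanism follows from the entry rule; the size does not. The odds ratios of 0.67 to 0.89 and the false-positive rates rest on assumed pain and numbness rates, on independence of the two, on an equal split of about 80 cases, and on an assumed 60% to 80% of foot-pain patients meeting HIV-SNP. The documents do not support saying that a sensory-loss factor will be reported as protective, only that its association with pain is pushed in that direction. This is a moderate matter that should be dealt with before analysis; it does not invalidate CHANT as a case definition.

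**What to change.** Keep CHANT as the main case definition. Pre-specify a repeat of the painful v painless contrast, and of neuropathy v none, with neuropathy defined without the pain item and from data already recorded: for example, bilateral signs regardless of symptoms. Symptom-free sign-positive patients then count as neuropathy and can serve as painless comparators.

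Base any claim that a factor is pain-specific or neuropathy-specific on the pain-free definition, and report the CHANT result beside it. Do not require a factor to hold under both: a true pain factor that the CHANT selection masks would then be rejected by the biased analysis. Numbness plus one sign is a weaker alternative, because painful, sign-positive patients who are not numb would be unassigned or fall among the comparators.

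Cost: one added analysis and no new data. Its case group departs from the validated CHANT definition and may differ in size.

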#### *g) Quantitative Sensory Testing (specific phenotyping)*

Quantitative Sensory Testing (QST) will be conducted the German Research Network on Neuropathic Pain QST protocol [10]. This is a battery of somatosensory testing which uses mechanical, cold, warm and pinprick stimuli in 13 domains; detection thresholds (cold detection threshold (CDT), warm detection threshold (WDT), paradoxical heat sensation (PHS), thermal sensory lime (TSL), mechanical detection threshold (MDT) and vibration detection threshold (VDT)), pain thresholds (cold pain threshold (CPT), heat pain threshold (HPT), mechanical pain threshold (MPT) and pressure pain threshold (PPT)), and stimulus-response functions (mechanical pain sensitivity (MPS), wind-up ration (WUR) and dynamic mechanical allodynia (DMA)).

Full QST testing has been performed on patients with HIV-SN in a previous study [14]. This study showed that although 86% of HIV-SN patients showed a loss of function in at least one modality, no single sensory parameter was had a useful diagnostic utility. This study showed that there were no significant differences in CPT, DMA, MPT and MPS between those with HIV-SN and healthy controls, and between those who reported pain and those that did not. Other studies have however, highlighted MPT and MPS as useful parameters [49] in HIV-SN. Therefore, in this study, the full DFNS QST protocol will be performed. The testing will be performed at the site of maximum pain or, in those with no pain, on the dorsum of their right foot, in the S1 dermatome.

QST results have been shown to differ in populations with cognitive impairment, such as Alzheimer's disease [63], but have not been assessed in comparison to mild cognitive impairment in HIV. It has however, been shown that there is good test-retest correlation when conducting QST in mild to moderate Alzheimer's, indicating that despite the requirement for short term memory and other executive functions, QST can still be performed in a reliable manner [63].

#### *h) Blood Testing*

A peripheral blood sample (30ml) will be taken from each patient.

10ml will be processed and stored as per protocol, from deCODE, and will be used for genetic analysis. Patients will be consented for using the blood for genetic analysis and that further genetic

or biochemical tests may be performed in the future on the sample to investigate potential links with pain, neuropathy or HAND. A material transfer agreement (MTA) will be in place between Imperial College London and deCODE in Iceland outlining the responsibilities of each party in the transfer of the blood samples. The remainder of the blood will be stored at Chelsea and Westminster Hospital until the end of the study. It will then be transferred to a secure tissue bank after processing at Chelsea and Westminster Hospital. This is for independent genetic or biochemical analysis in the future, for which patients will be fully consented.

*i) Conditioned Pain Modulation (Specific phenotyping)*

Conditioned Pain Modulation (CPM) is a method of testing a subject's intrinsic descending pain modulation. It is a way to measure the phenomenon that pain at one site can inhibit the sensation of pain at a distant site. It is thought that deficiencies in CPM exist in a number of chronic pain conditions such as fibromyalgia, diabetic polyneuropathy and osteoarthritis. The protocol for CPM has now been established in our laboratory. It involves using a warm thermode which is placed on the patient's forearm; the thermode is heated until the patient describes a pain score of 60 out of 100. This stimulus lasts for a maximum of 30 seconds. An alternative method is to use a pressure algometer to measure pain pressure threshold three times as a pressure test stimulus at the dominant upper arm (on the deltoid muscle). Either the thermal OR the pressure stimuli will be used, not both. Only patients unable to tolerate the pressure threshold will undergo thermal testing. The patient then is asked to place their hand in a bath of cold water (12°C) for one minute before the warm or pressure stimulus is repeated. The score the subject gives for the test stimulus before the cold stimulus is then subtracted for the score they give during the cold stimulus to give a value for 'CPM effect'. It is hypothesised that patients with pain will have a smaller CPM effect. To identify any placebo or nocebo effects from the cool water, the experiment will be repeated using room temperature water as a 'sham'.

Since subjects recruited up to the 30th October 2015 underwent the paradigm with the thermal test stimuli and the pressure pain threshold stimuli has been shown to be more reliable, patients tested between 1st December 2014 and 30th October 2015 will be invited to return to undergo the paradigm again, using the pressure pain threshold. Only patients who have indicated on their written consent form that they are happy to be contacted about future studies will be approached. They will be contacted by email or telephone and sent the additional patient information leaflet (PIL additional information version 1.0). At the clinical appointment they will undergo only CPM testing after signing a Consent Form Addendum (version 1.0). Reasonable travel expenses will be reimbursed.

*j) Hand Held Nerve Conduction Studies (Specific phenotyping)*

Formal nerve conduction studies (NCS) are used clinically to aid the diagnosis of small fibre neuropathy and are commonly used in the HIV population. However, formal NCS takes a considerable amount of time and must be performed at by a neurophysiologist at a specialist centre. Two new devices have been developed to identify sural nerve conduction abnormalities in a user-friendly way. These devices, the ADVANCE NCS System and the NC-Stat DPNCheck (both manufactured by Neurometrix) take only a couple of minutes and can be used by the non-expert. It involves passing an electric current through the ankle and measuring the speed and size of the nerve conduction of the sural nerve. These devices have been validated and are used clinically in the

diabetic population to detect a similar small fibre neuropathy to that seen in HIV patients. We intend to validate the use of these devices in HIV patients

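### One subtraction defines the CPM effect for both a heat pain rating and a pressure pain threshold, so inhibition takes opposite signs and different units

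*Combined protocol and SAP*

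**What the plan says.** All of this is in Section 3.3 i) of the combined protocol and SAP, unless another place is named.

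- **What CPM is.** It is described as inhibition: "pain at one site can inhibit the sensation of pain at a distant site".
- **Thermal test stimulus.** The recorded quantity is a rating: "the thermode is heated until the patient describes a pain score of 60 out of 100".
- **Pressure test stimulus.** The recorded quantity is a threshold: "An alternative method is to use a pressure algometer to measure pain pressure threshold three times as a pressure test stimulus". No unit is given.
- **Procedure.** The hand is in cold water "for one minute before the warm or pressure stimulus is repeated", so both stimuli follow the same sequence.
- **Derived value.** There is one rule. The score before conditioning, "before the cold stimulus is then subtracted for the score they give during the cold stimulus to give a value", yields the CPM effect.
- **Hypothesis.** "It is hypothesised that patients with pain will have a smaller CPM effect".
- **Who has which stimulus.** Pressure is now the default: "Only patients unable to tolerate the pressure threshold will undergo thermal testing". Subjects recruited up to 30 October 2015 "underwent the paradigm with the thermal test stimuli and the pressure pain threshold stimuli has been shown to be more reliable". Those tested from 1 December 2014 to that date are invited back for pressure testing, but only if they had agreed to further contact.

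Section 7.2 covers the genetic analysis and contains no CPM analysis. Section 2 e) places CPM in smaller embedded studies whose details are still to be confirmed, while Section 3.3 i) lists it as specific phenotyping.

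**The concern.** The two stimuli measure pain sensitivity in opposite directions. Less pain means a lower rating but a higher threshold. One subtraction therefore cannot give inhibition the same sign for both, and the results are in rating points for one stimulus and pressure units for the other.

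The description of CPM makes the intended meaning of a smaller effect clear: less inhibition. The signed value delivers that meaning for one stimulus only.

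Both kinds of value can remain in the data. Some patients cannot tolerate pressure, and some thermally tested patients will not have agreed to contact or will not return. Retested patients hold both values, and nothing says that the pressure value replaces the thermal one.

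An analyst who applies the written rule would have one stimulus running against the hypothesis. If the values were also put into one comparison, a real difference could be diluted or reversed, and unequal use of the thermal stimulus could create a false one.

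**Working it through.** The plan gives no effect size, SD, alpha or power for CPM, so there is no figure of its own to reproduce.

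**1. Sign and unit (no assumption about the thermal share).** The baseline rating of 60 is from Section 3.3 i); the changes are illustrative. The rule is read as during minus before.

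| Stimulus | More inhibition | Less inhibition | Which patient has the smaller signed value? |
|---|---|---|---|
| Thermal (rating points) | 45 - 60 = -15 | 55 - 60 = -5 | The more inhibited (wrong way) |
| Pressure (arbitrary units) | +40 | +10 | The less inhibited (as intended) |

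Reading the rule as before minus during flips every sign. Thermal then agrees with the hypothesis and pressure does not. The conflict remains on either reading.

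**2. Only if the stimuli were pooled.** Every input here is assumed:

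- The pain group has d = 0.5 SD less inhibition.
- The thermal share f is 10%, 20% or 30%, equal in both groups.
- The thermal change has mean mT = -10 and SD sT = 15.
- The pressure change has mean mP and SD sP, varied because the unit is unknown.

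*Standardised within stimulus, signs uncorrected.* The remaining difference is d(1 - 2f):

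- f = 0.1: 0.5 × 0.8 = 0.40 SD
- f = 0.2: 0.5 × 0.6 = 0.30 SD
- f = 0.3: 0.5 × 0.4 = 0.20 SD

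*Raw values.* The observed standardised difference (positive = expected direction) is

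d[(1-f)sP - f·sT] / √[(1-f)sP² + f·sT² + f(1-f)(mP - mT)²].

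For mP = 40, sP = 100 and f = 0.1, this is 0.5 × (90 - 1.5) / √(9000 + 22.5 + 225) = 44.25 / 96.16 = 0.460.

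| Pressure mean / SD | f = 0.1 | f = 0.2 | f = 0.3 |
|---|---|---|---|
| +40 / 100 | 0.460 | 0.419 | 0.376 |
| +40 / 60 | 0.445 | 0.390 | 0.336 |
| +4 / 6 | 0.229 | 0.088 | -0.013 |
| +0.4 / 0.6 | -0.084 | -0.159 | -0.214 |

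The wide spread comes mainly from the unknown pressure scale.

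*No true difference, unequal thermal shares.* Raw values were simulated and compared by a two-sample t-test at two-sided 5%, with 20 to 100 patients per group and 8,000 replicates. Across the four pressure scales, false positives were about 5-18% for 20% v 10% thermal, and about 6-49% for 30% v 10%.

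**The case against.** **The rule may cover only the thermal rating.** It speaks of a score that the subject gives, and the only such score described is the heat rating; a threshold is read from an algometer. On that view there is no sign conflict, only an omission. The reading is possible, but the preceding sentence repeats either stimulus, and pressure is itself called a test stimulus. If the narrow reading is right, the default stimulus has no rule at all, so the text still needs correcting.

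**The wording of the subtraction is unclear, and -5 is a smaller effect than -15 in magnitude.** Within one stimulus, a sign convention changes neither the size of a group difference nor a two-sided p-value. This is true, and it limits the harm under separate analysis to labelling and direction. It does not make the signed values agree across stimuli.

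**Pooling is not planned.** This stands. The retest suggests a move towards pressure alone, and the pooled figures rest wholly on assumed inputs. Separate analysis is not stated either.

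**Thermal data from before the re-invitation window are speculative.** This also stands: the documents do not say that any CPM test took place before 1 December 2014. Intolerance of pressure, lack of agreement to contact and failure to return remain as sources of thermal-only data.

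**Conclusion.** The concern holds, at minor severity. The stated rule gives opposite signs and different units for the two stimuli, and one of the two must run against the stated hypothesis. This needs no assumed share or SD. It rests on reading the rule as covering both stimuli, which the procedure supports; on the narrower reading, the default stimulus is undefined.

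Read as during minus before, pressure values are unaffected. Dilution, reversal and excess false positives depend on pooling, which is not stated, and on assumed inputs. No single figure for them is supported, because the thermal share, the pressure unit and the number of patients with CPM are not given. The sample size of 200 and the genetic objective are untouched.

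**What to change.** In Section 3.3 i), or in a short CPM analysis section:

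- Define the effect for each stimulus with inhibition positive: thermal = before minus conditioned; pressure = conditioned minus before.
- State the unit of each and how the three threshold readings are combined.
- State that a retested patient counts with the pressure value, which the protocol itself calls more reliable. Thermal values from the same patients can still serve a comparison of methods.
- Do not combine raw values across stimuli. Analyse the stimuli separately, or combine only effects standardised within stimulus.
- Reconcile two related points of wording: whether the repeat is scored during or after immersion, and the one-stimulus-only statement with the retest. Say also how the sham run enters the effect.

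The cost is wording and a little analysis work, with no new data. The thermal stratum may be small and imprecise.

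A pressure-only analysis loses some power. At an assumed 0.5 SD and two-sided 5%, with 10/20/30% thermal, power falls from about 70% to about 65/60/54% with 50 patients per group. With 100 per group it falls from 94% to about 92/88/84%. Combining correctly signed, standardised effects keeps about 68-70% and 93-95% respectively, but assumes the same standardised difference for both stimuli.
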